For cohort 2 after completion of the first single dose level the SRC will meet to review safety data from the single dose 1 (cohort 2) and the PK data (up to 24 hours post dose) from the single doses in cohort 1 as a minimum. The SRC will then determine whether it is safe to proceed to single dose 2 (cohort 2) and use available PK data, and emerging data from the AstraZeneca Global SAD/MAD Study to confirm the dose. After single dose 2 (cohort 2) a SRC will meet to review the available safety data from single doses 1 and 2 (cohort 2) to determine whether it is safe to proceed to multiple dose (cohort 2) and use the PK data available from single dose 1 (cohort 2) and cohort 1 (both single and multiple doses), and emerging data from the AstraZeneca Global SAD/MAD Study to confirm the dose. The SRC will also meet following the completion of the multiple dose (cohort 2) to review safety data, and PK data if available, for internal information.

Note: All safety and PK data from the current study will be reviewed blinded.

Figure 1 Study flow chart

[figure not shown]

Table 1 Study plan

Assessment	Visit 1a	Visit 1b	Visit 2	Visit 3	Visit 4	Visit 5
		Day -21 to -1	Day 1	Day 7	Day 13 to 19	Day 29 (+2 days)
Informed consent / enrolment	X					
Genetic consent	X					
Inclusion/Exclusion criteria		X	X			
Demographics		X				
Medical and surgical history		X				
Concomitant medication		X	X	X	X	X
Physical examination (inc. height and weight)		X	X ^{1,2}			X ²
Alcohol and drugs of abuse screen		X	X	X ³	X ³	X ³
Hepatitis B&C and HIV screen		X				
Safety bloods and urinalysis		X	X ⁴	X ⁴	X ⁴	X
12-Lead ECG (paper)		X	X	X	X ⁵	X
12-Lead ECG (digital)			X ⁶	X ⁶	X ⁶	
Telemetry			X ⁷	X ⁷	X ⁷	
Sitting blood pressure and pulse		X	X ⁸	X ⁸	X ⁸	X
Pregnancy test		X ⁹				
Adverse events		X	X	X	X	X
Randomisation			X			
AZD9668 or placebo administration			X	X	X	
Plasma PK profile			X ¹⁰	X ¹⁰	X ¹⁰	
Full urine collection (PK)			X ¹¹	X ¹¹	X ¹¹	
PD blood sample			X ¹²	X ¹²	X ¹²	
PGx blood sample			X ¹³			

¹ Abbreviated physical examination only.

² Weight only will be measured at this visit.

³ To be performed when volunteer returns to the [REDACTED] between study visits.

⁴ Pre-dose in each dosing period.

⁵ Paper ECGs recorded at the timepoints shown in Table 2, and at 48 and 72 hrs post dose at Visits 2, 3 and 4. If dECGs are to be performed each should be preceded by a paper ECG recording.

⁶ Digital ECGs (if required) will be performed at the times shown in Table 2.

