3.1.1 Stopping criteria for dose escalation

3.1.1.1 Safety Review Committee

Within each cohort dose escalation will only proceed once dosing has been completed at the previous dose level, however, it is possible that multiple dose (cohort 1) and single dose 1 (cohort 2) may run in parallel. For cohort 1, following completion of the first single dose level, the Investigator will review available safety data (blinded) to confirm that it is safe to proceed with the next single dose level. After the second single dose, a blinded Safety Review Committee (SRC) will meet to review the available safety data from single doses 1 and 2 to determine whether it is safe to proceed with the multiple dose in these individuals and the single dose 1 for cohort 2. The SRC will also review the PK data (up to 24 hours post dose as a minimum) from the single dose 1, and emerging data from the AstraZeneca Global SAD/MAD Study to confirm dose selection. Following the completion of the multiple dose, the SRC will review the available safety data from the multiple dose and the PK data (up to 24 hours post dose as a minimum) from the first two single doses.

For cohort 2 after completion of the first single dose level the SRC will meet to review safety data from the single dose 1 (cohort 2) and the PK data (up to 24 hours post dose) from the single doses in cohort 1 as a minimum. The SRC will then determine whether it is safe to proceed to single dose 2 (cohort 2) and use available PK data, and emerging data from the AstraZeneca Global SAD/MAD Study to confirm the dose. After single dose 2 (cohort 2) a SRC will meet to review the available safety data from single doses 1 and 2 (cohort 2) to determine whether it is safe to proceed to multiple dose (cohort 2) and use the PK data available from single dose 1 (cohort 2) and cohort 1 (both single and multiple doses), and emerging data from the AstraZeneca Global SAD/MAD Study to confirm the dose. The SRC will also meet following the completion of the multiple dose (cohort 2) to review safety data, and PK data if available, for internal information.

Note: All safety and PK data from the current study will be reviewed blinded.

The SRC will be chaired by an AstraZeneca Physician and will comprise the following individuals, as a minimum:

- AstraZeneca study team physician, or nominated deputy.
- AstraZeneca drug safety physician, or nominated deputy.
- AstraZeneca study team pharmacokineticist, or nominated deputy.

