3.1.1.2 Stopping criteria for dose escalation during the single dose phase

Escalation to the next dose level will not occur if any of the following criteria are met with the previous dose levels:

- Either an alanine aminotransferase (ALT) / aspartate aminotransferase (AST) level ≥ 3 x upper limit of normal (ULN) at two consecutive time points, or any pattern of liver function test (LFT) abnormalities giving cause for concern, in two or more volunteers on active treatment.

- Evidence of haemolysis as evidenced by the following in two or more volunteers on active treatment.
 - Reticulocyte count of over 5%, and,

At least two of the following:

- A drop in haemoglobin below 10.5 g/dL.
 - Decrease of 25% in haptoglobin. (The value post-dose to be compared with the average of two pre-dose values. The value should also be 15% below the lower limit of normal [LLN]).
 - Increase of 25% in unconjugated bilirubin or lactate dehydrogenase (LDH). (The value post-dose to be compared with the average of two pre-dose values. The value should also be 15% above ULN).
- A platelet count of below $80,000 \times 10^9/L$ confirmed by a repeat test (in the absence of obvious platelet clumping in a peripheral blood film) in two or more volunteers on active treatment.
 - A QTcF >500 ms in two or more volunteers on active substance (QT interval corrected for heart rate by Fridericia method) or a QTcF prolongation >60 ms on average, sustained for more than 30 minutes, ie, present on two contiguous timepoints, in two or more volunteers on active substance based on the results of the continuous readings compared to baseline.
 - Any general safety finding that in the opinion of the Investigator gives cause for concern.
 - Data indicate that at the next proposed dose, the geometric mean plasma C_{max} would be expected to exceed $2.5 \mu M$ or the geometric mean $AUC_{(0-24)}$ would be expected to exceed $18 \mu M.h$. If $AUC_{(0-24)}$ cannot be calculated $AUC_{(0-t)}$ will be used.

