3.1.1.3 Stopping criteria for dose escalation during the multiple dose phase

Escalation to the next dose level will not occur if any of the following criteria are met with the previous dose levels:

- Two or more volunteers on active treatment are discontinued because of either an ALT/AST level $\geq 3 \times ULN$ or any pattern of LFT abnormalities giving cause for concern.
- Evidence of haemolysis as evidenced by the following in two or more volunteers on active treatment.
 - Reticulocyte count of over 5%, and,

At least two of the following:

- A drop in haemoglobin below 10.5 g/dL.
 - Decrease of 25% in haptoglobin. (The value post-dose to be compared with the average of two pre-dose values. The value should also be 15% below LLN).
 - Increase of 25% in unconjugated bilirubin or LDH. (The value post-dose to be compared with the average of two pre-dose values. The value should also be 15% above ULN).
- A platelet count of below $80,000 \times 10^9/L$ confirmed by a repeat test (in the absence of obvious platelet clumping in a peripheral blood film) in two or more volunteers on active treatment.
 - A QTcF >500 ms in two or more volunteers on active substance (QT interval corrected for heart rate by Fridericia method) or a QTcF prolongation >60 ms on average, sustained for more than 30 minutes, ie, present on two contiguous timepoints, in two or more volunteers on active substance based on the results of the continuous readings compared to baseline.
 - Any general safety finding that in the opinion of the Investigator gives cause for concern.
 - Data indicate that at the next proposed dose the geometric mean steady state exposure ($C_{\max,ss}$ or $AUC_{(0-24),ss}$) will exceed 18 $\mu M.h$ and 2.5 μM , respectively.

Dosing in an individual volunteer may be discontinued in the multiple dose phase of the study (see Section 3.3.5.1 for criteria).

The stopping criteria refer to all volunteers at a specific dose level. In the event of the need to unblind the data for a given volunteer, or a given cohort, the study design will revert to a single blind study for that volunteer or cohort.

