3.3.5 Discontinuation of subjects from treatment or assessment

3.3.5.1 Criteria for discontinuation

Volunteers may be discontinued from study treatment and assessments at any time. Specific reasons for discontinuing a volunteer from this study are:

- Voluntary discontinuation by the volunteer, who is at any time free to discontinue his/her participation in the study without prejudice to further treatment.
- Safety reasons as judged by the Investigator and/or AstraZeneca.
- Severe non-compliance to protocol as judged by the Investigator and/or AstraZeneca.

- Incorrect enrolment ie, the volunteer does not meet the required inclusion/exclusion criteria for the study.
- Volunteer lost to follow-up.

Dosing will be discontinued in the multiple dosing period (ie, during Visit 4) if the criteria below are met:

- An ALT/AST level ≥ 3 x ULN or any pattern of LFT abnormalities giving cause for concern.
- Evidence of haemolysis as evidenced by the following in two or more volunteers on active treatment.
 - Reticulocyte count of over 5%, and,

At least two of the following:

- A drop in haemoglobin below 10.5 g/dL.
- Decrease of 25% in haptoglobin. (The value post-dose to be compared with the average of two pre-dose values. The value should also be 15% below LLN).
- Increase of 25% in unconjugated bilirubin or LDH. (The value post dose to be compared with the average of two pre dose values. The value should also be 15% above ULN).
- A platelet count of below $80,000 \times 10^9/L$ confirmed by a repeat test (in the absence of obvious platelet clumping in a peripheral blood film) in two or more volunteers on active treatment.
- A QTcF >500 ms in two or more volunteers on active substance (QT interval corrected for heart rate by Fridericia method) or a QTcF prolongation >60 ms on average, sustained for more than 30 minutes, ie, present on two contiguous timepoints, in two or more volunteers on active substance based on the results of the continuous readings compared to baseline.
- Any general safety finding that in the opinion of the Investigator or SRC gives cause for concern.

Specific reasons for discontinuing a volunteer from the genetic research when genetics is a secondary objective of the study are:

- Withdrawal of consent for genetic research. A volunteer may withdraw from this genetic research at any time, independent of any decision concerning participation

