3.4.3 Method of assigning subjects to treatment groups

Informed consent will be obtained before enrolment and the volunteers identified with an enrolment number starting with E0001001. Numbers will be allocated in ascending order.

Volunteers fulfilling the eligibility criteria will be assigned randomisation codes (unique volunteer numbers), starting with 100 (Japanese volunteers) and 200 (Caucasian volunteers). Numbers will be allocated in ascending order.

Volunteers will be assigned randomisation codes strictly sequentially as volunteers are eligible for randomisation. If a volunteer discontinues from the study the volunteer number will not be re-used and the volunteer will not be allowed to re-enter the study.

The randomisation schedule and associated individual treatment code envelopes (emergency unblinding tools) giving details of individual volunteer treatment will be produced by computer software (SAS[®]) that incorporates a standard procedure from generating randomisation codes.

Both Japanese and Caucasian volunteers will be allocated to either AZD9668 or placebo in a 6:2 ratio (AZD9668:placebo) per cohort. At each dose level, Japanese and Caucasian volunteers will be gender and age matched (± 5 years).

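### The platelet limit in three stopping rules is printed as 80,000 x 10^9/L, 1000 times the evident 80 x 10^9/L, so it cannot tell a low count from a normal one

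*Protocol*

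**What the plan says.** The same platelet criterion appears in three rules: the single dose escalation rule (Protocol 3.1.1.2), the multiple dose escalation rule (3.1.1.3) and the rule for discontinuing dosing during Visit 4 (3.3.5.1). In 3.1.1.3 it opens "A platelet count of below $80,000". In 3.1.1.2, with its unit, it reads "A platelet count of below $80,000 \times 10^9/L$ confirmed by a repeat test". The other two print the same number and unit.

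The criterion carries two further conditions. The count must be "confirmed by a repeat test (in the absence of obvious platelet clumping in a peripheral blood film"), and this must be seen in at least two volunteers on active treatment.

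The rules are binding. Under 3.1.1.2 and 3.1.1.3, any one criterion being met bars escalation. Section 3.3.5.1 says "Dosing will be discontinued in the multiple dosing period (ie, during Visit 4) if the criteria below are met". On scope, 3.1.1.3 says "The stopping criteria refer to all volunteers at a specific dose level".

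Three other provisions matter:

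- Volunteers are "allocated to either AZD9668 or placebo in a 6:2 ratio" within each cohort and ethnic group (3.4.3).
- Safety bloods at the dosing visits are taken "Pre-dose in each dosing period" (Table 1, note 4).
- Section 3.1.1.1 states "All safety and PK data from the current study will be reviewed blinded".

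**The concern.** The number belongs to one unit and the label to another. A limit of 80,000 is sensible per microlitre. With 10^9 per litre the matching number is 80. As printed, a normal count and a dangerously low one both fall below the limit, so the numerical part of the criterion does no work.

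What remains is the repeat test without clumping and the requirement for two active volunteers. If those are satisfied for any reason, the text requires escalation or dosing to stop whatever the counts are, and staff could go on only by departing from the approved protocol. Haematology is also a named concern for this drug: sections 1.1 and 3.2.2 report haematological changes in dogs at high doses. A pre-specified limit in this area should not depend on each reader correcting it silently.

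**Working it through.** The protocol gives no derivation of the limit, so there is no calculation of its own to reproduce. The check is a unit conversion followed by a reading of when the rule is met.

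**1. Unit conversion**

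- Printed: 80,000 x 10^9/L = 8 x 10^13/L.
- Evident intention: 80,000/µL x 10^6 µL/L = 8 x 10^10/L = 80 x 10^9/L.
- Ratio: 8 x 10^13 / 8 x 10^10 = 1000.

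**2. Other explanations for the figure**

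- A decimal comma (80.000) does not fit, because the protocol uses decimal points, for example 10.5 g/dL for haemoglobin in the same rules.
- An exponent misread in the PDF is conceivable, since 80,000 x 10^6/L would be exactly right. The same string in three separate sections makes this unlikely.
- Section 4.4.1 lists platelet count among the haematology variables but gives no unit, limit or reference range.

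**3. Distance from human counts.** The counts are assumptions; the protocol gives none.

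| Assumed count (x 10^9/L) | Printed limit / count |
|---|---|
| 100 (low end, healthy) | 80,000 / 100 = 800 |
| 500 (high end, healthy) | 80,000 / 500 = 160 |
| 2,000 (extreme) | 80,000 / 2,000 = 40 |

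The conclusion does not depend on the range chosen, because no plausible count comes near the limit.

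**4. What it takes to meet the literal rule**

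- Per dose level, over both ethnic groups: 8 + 8 = 16 volunteers, of whom 6 + 6 = 12 are on active treatment and 2 + 2 = 4 on placebo.
- The rule needs 2 of the 12, each repeat-tested without obvious clumping. Any two will do, since all counts are below the limit.
- Blinded review does not prevent this. Among 6 confirmed counts from the 16 volunteers, at most 4 are placebo, so at least 6 - 4 = 2 are active. Within one ethnic group of 8, 4 confirmed counts suffice: 4 - 2 = 2. Both figures take the 6:2 split as unchanged by replacements.

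**5. Which scheduled samples can start it.** Table 6 allows 5 haematology samples, which Table 1 places at Visits 1b, 2, 3, 4 and 5. Visits 1b and 2 precede any dose, and Visit 5 follows the cohort's last dose. Within a cohort this leaves 2: the pre-dose samples at Visits 3 and 4. For the Visit 4 dosing rule, the scheduled sample is therefore one taken before the first Visit 4 dose.

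**6. Printed and corrected limits compared.** With chance p that an active volunteer has a confirmed count below the limit, P(at least 2 of 12) = 1 - (1 - p)^12 - 12p(1 - p)^11.

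- Printed limit, once counts are repeated without clumping: p = 1, so the probability is 1.
- Limit of 80 x 10^9/L, assuming p between 0.001 and 0.01: 0.007% to 0.6%.

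**The case against.** The strongest reply is that the error would rarely bite. A repeat test and a clumping check make sense only after a suspiciously low count, so the sentence reveals its own intent. Nobody would routinely repeat normal counts, no repeat is scheduled, and without repeats even the literal criterion is never met. Experienced staff would probably read 80 x 10^9/L. No volunteer is endangered: a truly low count is below the printed limit too, and each rule also has a general criterion for any safety finding of concern to the Investigator.

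Most of this stands, and it limits the severity. The probability of 1 above holds only once repeats have been done. It is also fair that the two-sample figure applies within a cohort. Cohort 1 results inform cohort 2 decisions, so a cohort 1 Visit 5 sample could count there if available in time.

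The reply does not rescue the text. It relies on readers replacing the printed limit with another, in a rule whose purpose is to fix the limit beforehand. A repeat made for an unrelated reason, such as a doubtful sample, would count toward the literal criterion with a normal result.

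**Conclusion.** The concern holds. The platelet limit is wrong by a factor of 1000 in three binding safety rules, and as printed it cannot separate normal from low counts. The error is conservative: it can only add reasons to stop. It has no effect unless counts are repeat-tested without clumping in at least 2 of the 12 active volunteers at a dose level. It should be corrected, but it does not undermine the design.

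The conclusion rests on two things outside the text. The intended limit of 80 x 10^9/L is inferred from the number and unit, and the human platelet range is assumed. The first needs clinical confirmation; the second does not affect the result.

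**What to change.** Have the clinical team confirm the intended limit, then replace 80,000 x 10^9/L with 80 x 10^9/L in sections 3.1.1.2, 3.1.1.3 and 3.3.5.1. Keep the repeat-test, clumping and two-volunteer conditions as they are. The cost is a wording change in three places, with no effect on design, sampling or analysis.

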The proposed single dose levels will be 30 mg, 60 mg, 120 mg and 150 mg, although they may change with emerging data from this study. The top dose will be no higher than 150 mg as this is the maximum dose that was administered to healthy volunteers in the AstraZeneca Global SAD/MAD Study (AstraZeneca Protocol Number: D0520C00001 “A Phase I, Randomised, Double Blind, Placebo Controlled, 2-part Study to Assess the Safety, Tolerability and Pharmacokinetics of Single and Multiple Oral Doses of AZD9668 in Healthy Volunteers” Date: [REDACTED]) and was found to be safe. In addition, modelled PK data from the current study will ensure that the predicted geometric mean C_{max} and $AUC_{(0-24)}$ at the top dose will not exceed 2.5 μM or 18 $\mu\text{M}\cdot\text{h}$, respectively. The multiple doses for both cohorts 1 and 2 will be selected following a safety review meetings using emerging data from the current study and the AstraZeneca Global SAD/MAD Study The maximum multiple dose will be capped at a total daily dose of 140 mg. In addition, the emerging PK data from the current study will be modelled to ensure that for the highest dose given, the predicted geometric mean exposures (both $AUC_{(0-24),ss}$ and $C_{max,ss}$) will not exceed 2.5 μM or 18 $\mu\text{M}\cdot\text{h}$, respectively.

Duration of treatment

For each cohort of volunteers, the study will last a minimum of four weeks.

Variables

- Pharmacokinetic

Plasma concentration of AZD9668 is a primary outcome variable and concentration of AZD9668 in urine is a secondary outcome variable.

From these data, the following PK parameters will be derived:

Single dose - Day 1 and 7: C_{max} ; t_{max} ; $AUC_{(0-t)}$; AUC ; $AUC_{(0-12)}$; $AUC_{(0-24)}$; $t_{1/2}$; V_z/F ; CL/F ; CL_R ; A_e ; F_e

Multiple dose - Day 13: C_{max} ; t_{max} ; $AUC_{(0-12)}$; C_{12} ; A_e ; F_e . The A_e and F_e will be estimated using data from 0-12 hours

Day 19: $C_{min,ss}$; $C_{max,ss}$; $t_{max,ss}$; $AUC_{(0-t),ss}$; $AUC_{(0-12),ss}$; $AUC_{(0-24),ss}$; $AUC_{,ss}$; $V_z/F_{,ss}$; $CL/F_{,ss}$; $t_{1/2,ss}$; CL_R ; $A_{e,ss}$; $F_{e,ss}$; R_{ac} ; $C_{12,ss}$

- Pharmacodynamic

The PD outcome variables for AZD9668 are as follows:

Single and multiple dosing – Inhibition of NE activity following zymosan stimulation *ex vivo*.

- Safety

The safety outcome variables for AZD9668 are primary variable, and are as follows:

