Healthy, male or female (non-childbearing potential), Japanese or Caucasian volunteers will be included; safety, tolerability and PK data will be compared between these populations to enable inclusion of Japanese volunteers in the subsequent clinical development programme for AZD9668. To be considered as 'Japanese', both of the volunteer's parents and both sets of grandparents must be Japanese, the volunteer must have been born in Japan, have a valid Japanese passport, and must not have lived outside Japan for more than 8 years. These criteria ensure representative study population by excluding mixed race or naturalised Japanese living in the West.

The starting dose for cohort 1 will be 30 mg. This dose has been selected as a low dose that was found to be safe and well tolerated based upon the emerging draft data from the AstraZeneca Global SAD/MAD Study. It is proposed that the subsequent single doses will be 60 mg, 120 mg and 150 mg. These are proposed doses only and may change with emerging data from this study. The top dose will be no higher than 150 mg as this is the maximum dose that was administered to healthy volunteers in the AstraZeneca Global SAD/MAD Study and was found to be safe. In addition, modelled PK data from the current study will ensure that the predicted geometric mean C_{max} and $AUC_{(0-24)}$ at the top dose will not exceed 2.5 μ M or 18 μ M.h, respectively. These exposure limits have been determined by the AstraZeneca Human Exposure Limits Committee (HELCC) following a review of the data obtained in the 1-month toxicology studies in the rat and dog. The limits have been set based upon the exposures at the no observed adverse effect level (NOAEL) in rat (370 mg/kg), corrected for the differences in plasma protein binding between the species. The NOAEL in the rat has been used because the free exposures at this dose are lower than those obtained in the dog at the NOEL dose.

The multiple doses for both cohorts 1 and 2 will be selected following a safety review meetings using emerging data from the current study and the AstraZeneca Global SAD/MAD Study. The maximum multiple dose will be capped at a total daily dose of 140 mg. In addition, the emerging PK data from the current study will be modelled to ensure that for the highest dose given, the predicted geometric mean exposures (both $AUC_{(0-24),ss}$ and $C_{max,ss}$) will not exceed 2.5 μM or 18 $\mu\text{M}\cdot\text{h}$, respectively.

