3.4.2 Doses and treatment regimens

Tablets of AZD9668/placebo will be administered by the Investigator (or his qualified staff) on each dosing day. The study drug will be taken orally in an upright position with 240 mL of water and the volunteers must drink all the water.

Each volunteer will receive two ascending single doses (on Days 1 and 7) followed by multiple doses (twice daily each dose administered 12 hours apart) for 6 days (Days 13-18), and a final single dose on the morning of Day 19 (ie, a total of 15 doses).

The proposed single dose levels are 30 mg, 60 mg, 120 mg and 150 mg, although they may change with emerging data from this study. The top dose will be no higher than 150 mg as this is the maximum dose that was administered to healthy volunteers in the AstraZeneca Global SAD/MAD Study and was found to be safe. In addition, modelled PK data from the

current study will ensure that the predicted geometric mean C_{\max} and $AUC_{(0-24)}$ at the top dose will not exceed 2.5 μM or 18 $\mu\text{M}\cdot\text{h}$, respectively.

The multiple doses for both cohorts 1 and 2 will be selected following a safety review meetings using emerging data from the current study and the AstraZeneca Global SAD/MAD Study. The maximum multiple dose will be capped at a total daily dose of 140 mg. In addition, the emerging PK data from the current study will be modelled to ensure that for the highest dose given, the predicted geometric mean exposures (both $AUC_{(0-24),\text{ss}}$ and $C_{\max,\text{ss}}$) will not exceed 2.5 μM or 18 $\mu\text{M}\cdot\text{h}$, respectively.

Cohorts of Japanese and Caucasians healthy volunteers will receive the same dose of AZD9668, and will be run in parallel as far as is possible.

For the single doses, volunteers will be fasted from midnight the night before dosing day, except water for thirst. On waking on the morning of each dosing day volunteers will consume 150 mL of water. This must be a minimum of 1 hour before dosing. No further fluids will be allowed before dosing. Two hours post dose, volunteers will be provided with 200 mL of water. No food is allowed until 4 hours after dosing. Lunch will be served at approximately 4 hours post dose, and an evening meal between 8 and 10 hours post dose. From lunchtime onwards the volunteers will be allowed fluids and snacks within the restrictions of the study.

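### All five statements of the steady-state exposure limit swap the thresholds for Cmax,ss and AUC(0-24),ss, including the multiple-dose stopping rule

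*Protocol*

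**What the plan says.** The protocol limits steady-state exposure in two forms of words, in five places.

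- **Stopping rule, Section 3.1.1.3.** Escalation does not proceed if data indicate that, at the next proposed dose, the "geometric mean steady state exposure ($C_{\max,ss}$ or $AUC_{(0-24),ss}$) will exceed 18 $\mu M.h$ and 2.5" µM. The sentence closes with 'respectively'.
- **Cap on the multiple dose, in the Synopsis and Sections 3.1 and 3.2.1.** Modelling is to ensure, for the highest dose given, that "the predicted geometric mean exposures (both $AUC_{(0-24),ss}$ and $C_{max,ss}$) will not exceed 2.5" µM or 18 µM.h, again with 'respectively'. Section 3.4.2 repeats the sentence: "the predicted geometric mean exposures (both $AUC_{(0-24),\text{ss}}$ and $C_{\max,\text{ss}}$) will not exceed 2.5" µM or 18 µM.h, respectively.

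The single-dose limits use the same two values. Section 3.1.1.2 gives each parameter its own clause: "geometric mean plasma C_{max} would be expected to exceed $2.5 \mu M" for the peak, and "AUC_{(0-24)}$ would be expected to exceed $18 \mu M.h" for the area. The Synopsis and Sections 3.1, 3.2.1 and 3.4.2 also state the single-dose limits, as Cmax then AUC(0-24) against 2.5 µM then 18 µM.h.

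On the origin of the values, Section 3.2.1 says: "These exposure limits have been determined by the AstraZeneca Human Exposure Limits Committee", based on exposures at the rat no-observed-adverse-effect level corrected for protein binding.

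**The concern.** With 'respectively', the order of the parameters and the order of the values have to match. In every steady-state statement they do not. The peak is tied to a µM.h value and the area to a µM value, so the rule cannot be evaluated literally.

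The location matters. Section 3.1.1.3 is an operative stopping criterion, not background text. Together with the cap it forms the only exposure-based limit on multiple dosing. The separate 140 mg daily cap restricts dose, not exposure, and so does not respond to the PK seen in this study. One purpose of the study is to compare PK between Japanese and Caucasian volunteers. Section 3.2.1 also records that multiple dosing in the global study had only started, at 30 mg daily, when this protocol was written.

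A second fault sits in the same sentence of Section 3.1.1.3. The parameters are joined by 'or' and the values by 'and', which leaves it unclear whether exceeding one limit is enough.

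**Working it through.** The protocol gives no derivation of the limits to reproduce. The check is therefore one of units and order.

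**Units.** Cmax and Cmax,ss are concentrations, in µM. AUC(0-24) and AUC(0-24),ss are concentration × time, in µM.h. So 2.5 µM can only limit a Cmax, and 18 µM.h can only limit an AUC.

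**Steady-state statements, read in order**

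| Place | Parameters, in order | Values, in order | Pairing that results |
|---|---|---|---|
| Synopsis | AUC(0-24),ss; Cmax,ss | 2.5 µM; 18 µM.h | AUC to µM, Cmax to µM.h: transposed |
| Section 3.1 | AUC(0-24),ss; Cmax,ss | 2.5 µM; 18 µM.h | transposed |
| Section 3.1.1.3 | Cmax,ss; AUC(0-24),ss | 18 µM.h; 2.5 µM | Cmax to µM.h, AUC to µM: transposed |
| Section 3.2.1 | AUC(0-24),ss; Cmax,ss | 2.5 µM; 18 µM.h | transposed |
| Section 3.4.2 | AUC(0-24),ss; Cmax,ss | 2.5 µM; 18 µM.h | transposed |

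Correct: 0 of 5.

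**Single-dose statements, read in order**

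| Place | Cmax limit | AUC(0-24) limit |
|---|---|---|
| Synopsis, Sections 3.1, 3.2.1 and 3.4.2 | 2.5 µM | 18 µM.h |
| Section 3.1.1.2 | 2.5 µM | 18 µM.h |

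Correct: 5 of 5.

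The stopping rule lists both the parameters and the values in the opposite order from the cap. Two reversals cancel, so both forms of words give the same wrong pairing, and neither can be used to correct the other.

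**If the bare numbers were used and the units ignored**

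- Cmax,ss limit: 18 instead of 2.5, so 18 / 2.5 = 7.2 times too high.
- AUC(0-24),ss limit: 2.5 instead of 18, so too low by the same factor, 18 / 2.5 = 7.2.
- If exceeding either limit is enough, the false AUC limit is reached first unless AUC(0-24),ss / Cmax,ss is below 2.5 / 18 = 0.139 h, about 8 minutes. For a 24-hour area under twice-daily oral dosing that is not credible. The likelier result would be a needless halt, not over-exposure.

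This last step only gives the direction of the error under a misreading that the printed units argue against. It is not a predicted effect on dose.

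**The case against.** The strongest reply is that each value is printed with its unit, so each can belong to only one parameter. On that view no coherent wrong rule exists to be followed, and the only meaningful reading is the intended one. The correct single-dose rule stands in the section immediately before the stopping rule, and in the other four places the correct single-dose sentence comes shortly before the transposed one. The safety review committee includes a pharmacokineticist and a statistician. The 140 mg daily cap, the clinical stopping criteria and the investigator's discretion all apply independently. The five statements also come down to two drafting slips, one of them copied into four places.

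Most of this stands. Misapplication is unlikely, nothing is miscalculated, and the limit values are not in question.

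Two narrower points also stand. The single-dose and steady-state rules govern different parameters in different phases, so the single-dose text shows the intended pairing without strictly contradicting the other. And the sentence on the exposure limits committee follows the single-dose limits, so extending it to the steady-state limits is an inference from the identical values.

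The reply does not show that the text is right. No correct steady-state statement exists to defer to, and the units do nothing to settle the 'or'/'and' ambiguity.

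**Conclusion.** The error is real. All five steady-state statements are transposed, and one of them is an operative safety stopping criterion. It can be seen from the protocol alone, and it is not a PDF artefact: parameters, values, units and 'respectively' are legible in all five places, and the single-dose sentences in the same document read correctly.

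No effect on dose, design or analysis is claimed. The conclusion that 2.5 µM and 18 µM.h are the intended limits for Cmax,ss and AUC(0-24),ss rests on the units and on the matching single-dose limits. It should be corrected because a stopping threshold in healthy volunteers ought to be usable as written, without the reader having to override its wording.

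**What to change.** Give each parameter its own limit and drop 'respectively', following the form of Section 3.1.1.2.

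- **Section 3.1.1.3:** *the geometric mean Cmax,ss would exceed 2.5 µM, or the geometric mean AUC(0-24),ss would exceed 18 µM.h.* This also makes clear that exceeding either limit is sufficient.
- **Synopsis and Sections 3.1, 3.2.1 and 3.4.2:** *predicted geometric mean Cmax,ss will not exceed 2.5 µM, and predicted geometric mean AUC(0-24),ss will not exceed 18 µM.h.*

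The sponsor should confirm the pairing against the exposure limits committee's record when making the change. The cost is a wording amendment in five places; the limit values, the 140 mg cap, the design and the analysis stay as they are.
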